## Follow-Up Dates (vary by analysis/outcome)

### Treatment Outcomes

- Date of avacopan discontinuation (for time from initiation to discontinuation)
- Date of glucocorticoid discontinuation and usage patterns, including dosage changes (for time from initiation to discontinuation)
- 6 months after avacopan initiation (for primary outcomes at Month 6)
- 12 months after avacopan initiation (for primary outcomes at Month 12)

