### Clinical Outcomes

- Date of relapse (any and stratified by major or minor), (for time from initiation to relapse)
- Date of death (for time from initiation to death)
- Date of end of follow-up (for time from initiation to outcomes of interest)
- Date of loss to follow-up (for time from initiation to outcomes of interest)
- Date of adverse event or other event of interest in specific analyses (for time from initiation to adverse event)

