### **Study Sample Size**

- There are 133 patients identified through January 2024 from within the Mass General Brigham system who have been prescribed avacopan and 112 have initiated avacopan. Additionally, since December 1, 2021, there are 60 patients diagnosed with GPA/MPA in the MGB system who were not prescribed avacopan. Among those who have initiated avacopan, there have been 23 relapses. Glucocorticoid exposure has varied but the majority of patients have discontinued glucocorticoids within 2 months of avacopan initiation. There are only 2 patients in this cohort with missing status regarding avacopan initiation.

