### **Data Analysis**

- The primary and secondary outcomes will be analyzed using a descriptive approach. Summary statistics for continuous variables, including the number of patients, mean, standard deviation (SD), median, Q1, Q3, minimum and

maximum, will be calculated after excluding missing/unknown values. For categorical variables, the frequency and percentage will be provided, and a category of “missing/unknown” will be included. Cumulative incidence will be used to describe the occurrence of key outcomes, including glucocorticoid toxicities, infections, and relapse. Given the variable follow-up time, healthcare resource utilization (HCRU) and costs will be presented as per patient per month (PPPM) metrics. Time to event outcomes (e.g., time to discontinuation of glucocorticoids) will be calculated using Kaplan-Meier analysis and median follow-up time (interquartile range [IQR]) will be reported.

- Among avacopan users, we will consider analyses evaluating time to events (e.g., glucocorticoid discontinuation, relapse) with adjustment for covariates. We will consider Cox proportional hazard regression models or other methods for time to event analyses and incorporate covariates, considering the number of observed outcomes. Restricted mean survival time will be used to describe time free from glucocorticoid exposure during follow-up.
- Among avacopan users, exploratory analysis of the association of glucocorticoid exposure with the risk of relapse will be assessed using an emulated target trial framework with a clone, censor, weighting approach. Cluster analysis will be used to explore patterns of glucocorticoid prescribing for patients using avacopan. Cox proportional hazards models will be used to evaluate factors associated with the risk of relapse and factors associated with glucocorticoid discontinuation.

CCI

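### Restricted mean survival time summarises one event, so applied to glucocorticoid discontinuation, the only glucocorticoid event the protocol defines, it does not measure total glucocorticoid-free time

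*Protocol*

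**What the plan says.** The Data Analysis section of the protocol makes a firm commitment: "Restricted mean survival time will be used to describe time free from glucocorticoid exposure during follow-up". The sentence gives no event, time origin, horizon, or rule for restarts or deaths.

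The surrounding text points to one glucocorticoid event, discontinuation. The same section says "Time to event outcomes (e.g., time to discontinuation of glucocorticoids) will be calculated using Kaplan-Meier analysis". Under Follow-Up Dates, Treatment Outcomes, the relevant entry is "Date of glucocorticoid discontinuation and usage patterns, including dosage changes (for time from initiation to discontinuation". It covers usage patterns and dose changes but does not name a restart date. Under Clinical Outcomes, death appears as its own endpoint, "Date of death (for time from initiation to death", with no statement of how it enters the glucocorticoid analysis.

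Study Sample Size supplies the relevant facts on the cohort: of 133 patients "who have been prescribed avacopan and 112 have initiated avacopan"; "Among those who have initiated avacopan, there have been 23 relapses"; and "the majority of patients have discontinued glucocorticoids within 2 months of avacopan initiation".

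**The concern.** The method and the target do not match. RMST is the area under a survival curve for one event up to a horizon. Time off glucocorticoids is time spent in a state that can be entered, left and entered again, and that death ends. The two coincide only when nobody restarts and nobody dies within the horizon.

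The protocol's own figures make restarts foreseeable. Most initiators stop glucocorticoids early, and 23 relapses have been recorded among 112 initiators, so many of those relapses could fall after the first stop. At stake is a descriptive figure that readers will take as how long patients on avacopan live without glucocorticoids. It could be wrong in either direction, depending on which event the analyst picks.

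**Working it through.** The protocol states no RMST value or horizon, so there is no figure to reproduce. The check asks how far each single-event version departs from actual time alive and off glucocorticoids.

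**Inputs from the protocol**
- Relapses: 23/112 = 20.5 per 100 initiators. This is treated as 20.5% of patients relapsing by Month 12, with relapses starting after Month 1, when the protocol begins to assess them. The monthly hazard is −ln(1 − 0.205)/11 ≈ 0.021.
- Time to first stop: a majority by 2 months means a median of at most 2 months. Medians of 1 and 2 months are used, with an exponential distribution.
- Horizon: 12 months, borrowed from the Month 12 outcomes ("12 months after avacopan initiation (for primary outcomes at Month 12").

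**Assumptions without a source in the protocol**
- Share of post-stop relapses leading to a restart: 0, 50 or 100%.
- Length of the restarted course: 3 or 6 months.
- 12-month mortality: 0, 3 or 5%.

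**Quantities compared**
- A = 12 − RMST of first stop, Kaplan-Meier, deaths censored.
- B = mean time alive and off glucocorticoids within 12 months (the target).
- C = mean length of the first glucocorticoid-free spell, from stop to restart, death or Month 12, averaged over all initiators.

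**Closed form for A.** With rate λ = ln 2 / median, RMST = (1 − e^(−12λ))/λ.
- Median 2: λ = 0.3466, RMST = 2.885 × (1 − 0.0156) = 2.84, so A = 12 − 2.84 = 9.16 months.
- Median 1: λ = 0.6931, RMST = 1.443 × (1 − 0.0002) = 1.44, so A = 12 − 1.44 = 10.56 months.

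The RMST itself (1.44 or 2.84 months) is mean time on glucocorticoids, the opposite of what the sentence sets out to describe. Only its complement has the right sign.

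**Simulation (200,000 patients per row, months; differences taken before rounding)**

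| Median stop | Restart share | Course | Mortality | A | B | A − B | C | C − B |
|---|---|---|---|---|---|---|---|---|
| 2 | 0% | – | 0% | 9.16 | 9.16 | 0.00 | 9.16 | 0.00 |
| 2 | 0% | – | 5% | 9.16 | 8.89 | 0.27 | 8.89 | 0.00 |
| 2 | 50% | 3 | 0% | 9.17 | 8.95 | 0.21 | 8.74 | −0.21 |
| 2 | 100% | 3 | 0% | 9.15 | 8.73 | 0.42 | 8.32 | −0.41 |
| 2 | 100% | 6 | 5% | 9.16 | 8.22 | 0.94 | 8.09 | −0.14 |
| 1 | 0% | – | 5% | 10.56 | 10.27 | 0.29 | 10.27 | 0.00 |
| 1 | 100% | 3 | 0% | 10.55 | 10.06 | 0.49 | 9.53 | −0.53 |
| 1 | 100% | 6 | 0% | 10.56 | 9.72 | 0.84 | 9.53 | −0.20 |
| 1 | 100% | 6 | 5% | 10.56 | 9.45 | 1.10 | 9.26 | −0.19 |

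**Reading the table**
- A exceeds B by 0 to 0.94 month with a median stop of 2 months, and by 0 to 1.10 months with a median of 1 month. The largest relative error is 1.10/9.45 = 12%.
- Deaths alone (3 to 5%) account for 0.2 to 0.3 month. Restarts alone account for 0.2 to 0.8 month.
- C never exceeds B. It falls short by up to 0.53 month, because glucocorticoid-free time after the restarted course is lost.
- Both errors vanish only when there are no restarts and, for A, no deaths.

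**The case against.** The strongest objection is that the protocol never says RMST will be run on first discontinuation, never says deaths will be censored there, and never says that restarts or time after death count as glucocorticoid-free. A reader might infer all of this by joining the RMST sentence to the Kaplan-Meier sentence, and conclude that the plan overstates glucocorticoid-free time in the drug's favour. The documents do not support that as an unconditional claim: starting the clock at the stop and ending it at restart or death is also a natural reading, and it errs the other way.

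A related objection is that this text sits in the Abstract, that fuller sections are blacked out, and that a statistical analysis plan may define event, horizon and handling of death. That is fair for those details, and their absence is not the point here. What remains is the pairing of method and target. Whatever horizon is chosen, RMST on one event does not add up several glucocorticoid-free spells, so a later document would have to change the estimand or the estimator.

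It is also true that the plan is not blind to re-exposure. Cumulative exposure, median daily dose and cluster analysis of prescribing patterns all reflect restarts, and both primary proportions consider glucocorticoid use in the month before the assessment. This limits the harm but does not correct the RMST figure.

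Finally, the size rests on assumptions. The 23 relapses are a raw count through January 2024 over unequal follow-up and may not be 23 different patients; not every relapse need follow a stop or lead to a restart. Assuming 12-month restart courses and 10% annual mortality could push the overstatement to about 1.4 months (18%), but nothing in the documents supports those values. The narrower range above is also illustrative, and it includes zero.

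**Conclusion.** The point holds in conditional form. The protocol commits to a single-event summary for a quantity that is time in a recurrent state, and discontinuation is the only glucocorticoid event it defines. Over 12 months, on the assumptions listed, the complement of RMST on discontinuation would overstate by about 0 to 1.1 months (0 to 12%), while RMST from stop to restart or death would understate by about 0 to 0.5 month. The direction cannot be settled from the protocol. What can be said is that neither version recovers total glucocorticoid-free time once patients restart and stop again.

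The consequence is modest. According to Hypothesis(es)/Estimation, outcomes are described and not tested. The analysis of initiators has no comparator, and RMST plays no part in the two primary proportions. The sentence should be corrected, but the study's main results do not depend on it.

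**What to change.** Replace the RMST sentence with a stated estimand: the restricted mean time alive and off glucocorticoids up to 6 and 12 months after avacopan initiation. Estimate it as the area under the state-occupancy curve for being off glucocorticoids, using the Aalen-Johansen estimator. Allow moves from on to off and back, treat death as an absorbing state, censor at loss to or end of follow-up, and give a bootstrap 95% CI. Report first discontinuation separately, as a cumulative incidence with death as a competing event.

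State also that restart dates will be derived from the usage-pattern and dosage-change data. The Treatment Outcomes list does not name them, so they should be made an explicit item in the chart abstraction. Death dates are already listed under Clinical Outcomes.

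The cost is some additional analysis work, care in deriving restarts from the chart, and possibly a slightly less favourable figure than the first-stop version would give. The cohort and the primary outcomes do not change.
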